## Overview

Laparoscopic hernia mesh fixation has become more commonplace worldwide for abdominal herniorrhaphy since first demonstrated in the early 1990's [1] [2]. Mesh fixation by this technique typically requires the use of a mechanical fastener, such as suture or a screw-like tack to physically attach the mesh to the abdominal wall. While providing strong fixation, permanent metal fasteners have been associated with high instances of chronic pain and other complications. Absorbable fasteners have been more recently developed as alternatives to permanent devices, however chronic pain continues to be an issue due to the associated penetration of abdominal tissues [2]. Surgical adhesives have recently been promoted as an alternative to mechanical fasteners due to their strong adhesive properties, without tissue penetration. These adhesives have been used as alternatives to other penetrative wound closure methods such as sutures and staples in topical wound closure since the late 1990's [3]. Most commonly formulated from cyanoacrylate polymers, these adhesives rapidly polymerize in contact with moisture on the skin to bond opposing sides of a wound forming an effective and durable wound closure. The LiquiBand FIX8® device incorporates a similar cyanoacrylate adhesive formulation, packaged in a laparoscopic delivery instrument to provide internal mesh and peritoneal tissue fixation as opposed to topical wound closure. LiquiBand FIX8® obtained CE-marking for approval in the European Union in 2014 for inguinal hernia mesh fixation and is now approved for peritoneal closure in addition to other indications. In addition to the EU, LiquiBand FIX8® is approved for use in multiple other countries worldwide including Australia, Canada, Israel and the United Arab Emirates. Independent evaluations of the LiquiBand FIX8® device have found it to be safe and effective for hernia mesh fixation and peritoneal closure, and although the authors stated the low occurrence of complications, the limited scope of these studies did not include a detailed review of post-operative pain [4] [5] [6] [7] [8] [9] [11]. In this study, further evaluation of the clinical performance and safety of the LiquiBand FIX8® device is proposed, including the detailed assessment of any long term post operative pain and other complications experienced by study subjects.

## CLINICAL INVESTIGATION SUMMARY

|                                |  |
|--------------------------------|--|
| Study Title:            | A multi-center, randomized, controlled, single blinded, parallel-group study evaluating the clinical performance and safety of LiquiBand FIX8® versus control for hernia mesh fixation and peritoneal closure in groin hernia repair.  |
| Investigational Device: | LiquiBand FIX8® Hernia Mesh Fixation Device  |
| Device Description:     | 
The device consists of:
 

a) n-butyl-2-cyanoacrylate adhesive monomer, in liquid form, supplied in a thin-walled, sealed glass vial; and,

b) a surgically invasive, laparoscopic 5mm diameter cannula, with a handle at the proximal end incorporating a loading chamber, filter, piston chamber and trigger. The distal tip of the device is open to allow the adhesive to be dispensed from it.

   |
|                                | 
The device is designed to be used in conjunction with a 5 mm diameter laparoscopic port sleeve. Both the cyanoacrylate adhesive in the glass vial and the surgically invasive delivery device are supplied sterile, for single use only.
  |
| Indication for Use:     | The LiquiBand FIX8® device is intended for use in laparoscopic surgical repair of groin (femoral and inguinal) hernias, achieved through the fixation of prosthetic mesh to the abdominal wall and the approximation of peritoneum.  |
| Design:                 | Prospective, two-arm, randomized, single blinded, multi-center study.  |
| Purpose:                | To demonstrate the efficacy and safety of LiquiBand FIX8® for groin hernia repair.   |
| Objectives:             | 
Primary:
 

1. To compare the improvement in pain following groin hernia repair by LiquiBand FIX8® to control device as measured by Visual Analog Scale (VAS) at baseline (worst pain experienced within 1 month of screening visit) and at six months post hernia repair.

 
Secondary:
 

1. To evaluate the incidence of hernia recurrence in patients following laparoscopic (TEP and TAPP) hernia repair using LiquiBand FIX8® or control device at 6 months post hernia repair.

2. To compare the use of LiquiBand FIX8® to control device for mesh fixation at time of surgery.

3. To compare the use of LiquiBand FIX8® to control devices for the approximation of the peritoneum (TAPP repairs only) at time of surgery.

4. To evaluate the quality of life experienced by subjects following groin hernia repair by LiquiBand FIX8® or control as measured by the Carolinas Comfort Scale (CCS) at baseline (prior to surgery), and at 1 week, 2 weeks, 1 month, 3 months, 6 months, 9 months and 12 months following surgery.

 |

5. To compare levels of pain experienced following laparoscopic (TEP and TAPP) groin hernia repair by LiquiBand FIX8® or control device, as measured by VAS at discharge, and at 1 week, 2 weeks, 1 month, 3 months, 6 months, 9 months and 12 months following surgery.
6. To evaluate the safety of LiquiBand FIX8® and control device for groin hernia repair by comparing incidence of all adverse events in patients post laparoscopic groin hernia repair.

**Number of patients:** 284 (142 per treatment arm)

**Investigational centers:** Up to 10 investigational centers will be recruited for this study, including the following institutions:

1. University of Kentucky
2. The Ohio State UniversityPrisma Health – Upstate
3. Overlake Medical CenterCleveland Clinic
4. Prisma Health – Upstate
5. Overlake Medical Center
6. Cleveland Clinic

**Study Hypothesis**

The study hypothesis is that the LiquiBand FIX8® device is non-inferior to a tack-based control device (AbsorbaTack™) for the laparoscopic (TEP and TAPP) repair of groin hernia. Non-inferiority will be demonstrated in a primary efficacy endpoint of improvement (decrease) of pain scores, measured by Visual Analog Scale (VAS), between baseline (worst pain experienced within 1 month of screening visit) and 6 months post-operatively.

## INCLUSION/EXCLUSION

### Inclusion Criteria

1. Patients who meet all the following criteria at the time of enrollment may be included:
2. Is male or female,  $\geq 22$  years of age
3. Is willing and able to give written informed consent
4. Has a primary or recurrent groin hernia (unilateral or bilateral, inguinal or femoral)
5. Is currently scheduled and eligible for TAPP or TEP laparoscopic groin hernia repair (inguinal or femoral)
6. Hernia mesh to be used at the time of surgery is at least 4" x 6" in size and is one of the following:
  - a. 3D Max™ Mesh (Bard Inc.)
  - b. 3D Max™ Light (Bard Inc.)
  - c. Parietex™ 2D (order code starting with TEC) Flat Sheet Mesh (Medtronic)
  - d. Parietex™ 3D (order code starting with TET) Flat Sheet Mesh (Medtronic)
7. Is willing and able to comply with the protocol assessments at time of surgery and during the post surgical follow up period

### Exclusion Criteria

1. Patients who meet any one of these criteria will be excluded from the investigation:
2. Has a hernia type not suitable for laparoscopic hernia repair as determined by the Investigator (i.e. strangulated)
3. Subject has a recurrent groin hernia previously repaired laparoscopically, has an anatomical defect or had prior surgical procedures that in the opinion of the Investigator prevents access to the pre-peritoneal space for TAPP or TEP laparoscopic hernia repair
4. Is pregnant or actively breastfeeding
5. Has a known sensitivity to cyanoacrylate or formaldehyde, D&C Violet No.2 dye or any component of LiquiBand FIX8® or control device
6. Has an active or potential infection at the surgical site or systemic sepsis
7. Hernia mesh to be used at surgery is less than 4" x 6" in size, or not one of the types of mesh listed in Inclusion Criteria #5.
8. Cannot tolerate general anaesthesia
9. Has any significant or unstable medical or psychiatric condition that, in the opinion of the Investigator, would interfere with his/her ability to participate in the study.
10. Is currently enrolled in another clinical study or undergoing treatment with another investigational drug or device.

## ENDPOINTS

**Table 1:** Primary and Secondary Efficacy and Safety Endpoints of the Investigational Study

| Table 1: Primary and Secondary Efficacy and Safety Endpoints of the Investigational Study |   |
|--|---|
| Primary Efficacy 1   | Effectiveness of LiquiBand FIX8® will be assessed and compared to treatment with AbsorbaTack™ in subjects requiring laparoscopic (TEP and TAPP) hernia repair. Success will be determined by improvement in pain not inferior to control device as measured by a VAS value (0 = no pain to 10 = most pain imaginable) from baseline (worst pain experienced within 1 month of screening visit) to six months post hernia repair.  |
| Secondary Efficacy 1   | The incidence of hernia recurrence in patients following laparoscopic (TEP and TAPP) groin hernia repair by LiquiBand FIX8® or control (AbsorbaTack™) will be assessed by physical examination at 2 weeks, 3 months, and 6 months and evaluated following the 6 month timepoint. Suspected hernia recurrence will also be evaluated at any time following surgery and up to the 12 month follow up visit if reported by the subject. Suspected hernia recurrence will be confirmed by ultrasound imaging following physical examination.  |
| Secondary Efficacy 2   | LiquiBand FIX8® will be required to successfully fix hernia mesh in patients undergoing TEP and TAPP laparoscopic groin hernia repair, at a rate non-inferior to control device (AbsorbaTack™) in order to meet this end point. Successful mesh fixation would not require any additional fixation by alternate fixation device. Unsuccessful mesh fixation is defined as requiring the use of an alternative fixation device or additional procedure to achieve adequate fixation.   |
| Secondary Efficacy 3   | LiquiBand FIX8® will be required to successfully approximate the peritoneum in patients undergoing laparoscopic TAPP hernia repair, at a rate non-inferior to control devices in order to meet this end point. Successful peritoneal closure would not require any additional fixation by alternate fixation device or additional procedure. Unsuccessful peritoneal closure is defined as requiring the use of an alternative fixation device or additional procedure to achieve adequate fixation. Investigators in the study will be able to use AbsorbaTack™, sutures or staples for closure of the peritoneum. |
| Secondary Efficacy 4   | Quality of Life will be assessed by completion of the Carolinas Comfort Scale (CCS) Questionnaire prior to surgery and at 1 week, 2 weeks, 1 month, 3 months, 6 months, 9 months and 12 months following laparoscopic (TEP and TAPP) groin hernia repair. CCS scores at each timepoint will be compared between the LiquiBand FIX8® and control (AbsorbaTack) treatment groups.   |
| Secondary Efficacy 5   | Evaluation of pain will be measured by VAS (0 = no pain to 10 = most pain imaginable) at baseline (pre-surgery), at discharge, and at 1 week, 2 weeks, 1 month, 3 months, 6 months, 9 months and 12 months post surgery.  |
| Secondary Safety 1   | The incidence of all adverse events whether or not determined to be related to the LiquiBand FIX8® device or control device (AbsorbaTack™) will be assessed intraoperatively, at discharge, and at each follow-up visit throughout the study, or for cause at any time in the follow up period.   |

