| Randomization                                |             | X  |                |                     |         |         |         |           |           |           |   |                   |
| Hernia Information (type & size)                         | X           | X  |                |                     |         |         |         |           |           |           |   |                   |
| Use of Investigational or control device                 |             | X  |                |                     |         |         |         |           |           |           |   |                   |
| Number of Investigational or control device applications |             | X  |                |                     |         |         |         |           |           |           |   |                   |
| Photograph following mesh fixation                       |             | X              |                |                     |         |         |         |           |           |           |   |                   |
| Photograph following peritoneal closure      |             | X              |                |                     |         |         |         |           |           |           |   |                   |
| Clinician evaluation of hernia repair & PE   |             |                |                |                     | X       |         | X       | X         |           |           |   | X                 |
| Subject Pain (0-10 VAS) Assessment                       | X           |                | X              | X                   | X       | X       | X       | X         | X         | X         |   |                   |
| Subject QOL Assessment                                   | X           |                |                | X                   | X       | X       | X       | X         | X         | X         |   |                   |
| AE Evaluation  |             | X  | X              | X                   | X       | X       | X       | X         | X         | X         | X |                   |

Immediately prior to surgery

During surgery

At discharge post-surgery, either on same day as surgery or next day post-surgery according to standard of care

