Height only required at Pre-surgery visit. Unless Pre-surgery (Visit 1), Surgery (Visit 2) and Discharge (Visit 3) occur on the same date, weight should be obtained for each separate visit. Vital signs may be obtained remotely at Month 3 and 6 visits as volunteered by subjects using their own devices as available (e.g. thermometer, weight scales, smart wearable technology)

Patient must be blinded to the randomized device

Photograph following peritoneal closure only required for TAPP repairs

Suspected hernia recurrence will be confirmed by ultrasound imaging following physical examination

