## Statistical Analysis

### General Approach

The primary efficacy endpoint will be tested for non-inferiority of treatment to control with a predefined non-inferiority margin of 0.9 on the VAS scale. Confounding factors for the pain score including analgesic use or other pain management therapies will be measured at screening and all follow up visits, and compared between treatment arms to ensure proper balance within each site. The study will be claimed successful if both PP and ITT analyses on the primary efficacy endpoint showed significance at 0.025. Once the hypothesis tests succeed for both analysis sets on the primary efficacy endpoint, key secondary endpoints will be compared between treatments sequentially in a non-inferiority manner. The following sequential analysis approach will be taken:

- Primary non-inferiority on the PP set; if significant at one-sided alpha=0.025, and
- Primary non-inferiority on the ITT set; if significant at one-sided alpha=0.025, then proceed to key secondary endpoints detailed in Section 3.1.
- Secondary non-inferiority on the PP set on Hernia Recurrence rate in subjects following laparoscopic (TEP and TAPP) groin hernia repair by LiquiBand FIX8® or control (AbsorbaTack™) at 6 months, at one-sided alpha=0.025.
- Secondary non-inferiority on the PP set on Rate of successful hernia mesh fixation in subjects undergoing TEP and TAPP laparoscopic groin hernia repair; if significant at one-sided alpha=0.025, then
- Secondary non-inferiority on the PP set on Rate of successful peritoneal closure in subjects undergoing laparoscopic TAPP hernia repair; if significant at one-sided alpha=0.025, then

The family-wise type I error will therefore be controlled at 0.025.

Summary statistics will consist of the number and percentage of responses in each category for discrete variables, and the mean, median, standard deviation (SD), minimum, and maximum for continuous variables. One-sided statistical tests will use a significance level of  $\alpha = 0.025$ , and two-sided tests will use a significance level of  $\alpha = 0.05$ .

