### **Analysis of the Secondary Endpoints**

The following safety and clinical outcomes will be evaluated.

The safety and clinical outcomes assessments include:

1. Hernia recurrence up to 12 months following surgery.
2. Hernia mesh fixation at time of surgery.
3. Approximation of the peritoneum at time of surgery (TAPP repairs only).
4. Quality of Life following groin hernia repair as measured by Carolinas Comfort Scale at baseline and at 7 days, 14 days, 1 month, 3 months, 6 months, 9 months and 12 months following laparoscopic (TEP and TAPP) groin hernia repair.
5. Subject pain following groin hernia repair as reported by VAS at screening, discharge and at 7 days, 14 days, 1 month, 3 months, 6 months, 9 months and 12 months following surgery.
6. Rate of device and procedure-related adverse events reported throughout the duration of the study.

To test the secondary endpoints #1, 2, and 3, a binomial non-inferiority test will be run using SAS Proc Freq with the Farrington-Manning method on the PP set. A p-value of  $< 0.025$  from the binomial non-inferiority test will be considered evidence that LiquiBand FIX8® is not inferior to AbsorbaTack™. Confidence interval on the difference of the rates will be reported and non-inferiority is indicated if the upper limit of the confidence interval is less than the non-inferiority margin. ITT analyses will be performed for the three secondary endpoints with hypothesis statements as supporting sensitivity analyses.

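### The supplied text masks neither the examiner nor the ultrasound reader for 6-month recurrence, so recurrences the subject does not report, or that are dismissed at examination, could be missed unequally between arms.

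*Combined protocol and SAP*

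**What the plan says.** **Blinding.** The Clinical Investigation Summary gives the design as "Prospective, two-arm, randomized, single blinded, multi-center study". The only blinding instruction is footnote 5 of the Schedule of Study Assessments: "Patient must be blinded to the randomized device".

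**Finding a recurrence.** Table 1, Secondary Efficacy 1, gives two routes.
- At scheduled visits, recurrence "will be assessed by physical examination at 2 weeks, 3 months, and 6 months and evaluated following the 6 month timepoint". The schedule lists this as "Clinician evaluation of hernia repair & PE", without saying who the clinician is or whether that person may know the device.
- Between or beyond those visits, a report from the patient can start an evaluation: "Suspected hernia recurrence will also be evaluated at any time following surgery and up to the 12 month follow up visit if reported by the" (the sentence ends by naming the patient).

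**Confirming it.** Table 1 and footnote 7 both say: "Suspected hernia recurrence will be confirmed by ultrasound imaging following physical examination". Ultrasound is not planned for every subject, and no criterion defines a suspected recurrence.

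**Testing it.** Under Statistical Hypotheses the margin is 10 percentage points, LiquiBand minus control. General Approach places recurrence first among the key secondary tests, "at 6 months, at one-sided alpha=0.025". Under Analysis of the Secondary Endpoints, "a binomial non-inferiority test will be run using SAS Proc Freq with the Farrington-Manning method on the PP set", with ITT as support.

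**The concern.** Because ultrasound follows suspicion, it can remove false positives but cannot recover a recurrence that was never referred. Whether a doubtful finding is referred is left to an examiner whom the supplied text does not mask. If examiners who know the device refer less readily in one arm, the detected rates differ for a reason unrelated to the device.

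The consequence is not symmetrical. Recurrences missed in the LiquiBand arm lower that arm's observed rate and make non-inferiority easier to declare; misses confined to control make it harder. The supportive ITT analysis offers no protection, because it uses the same detected events as the PP analysis. What is at stake is a confirmatory secondary claim.

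**Working it through.** The plan states no expected recurrence rate, so there is no planned figure to reproduce for this endpoint. The check asks how far unequal detection moves the error rate of the planned test.

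**Inputs from the plan.** Margin 0.10; one-sided alpha 0.025; Farrington-Manning test; 284 subjects (142 per arm); at least 226 evaluable at 6 months. The 226 is stated for VAS and is taken here as 113 per arm.

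**Assumptions.** True control recurrence 3%. True LiquiBand recurrence 13%, so the true difference is exactly 10 points and any claim of non-inferiority is false. A share s_T of LiquiBand recurrences and s_C of control recurrences is detected. Ultrasound removes every false positive.

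**Formulas.** Observed event probabilities are 0.13 × s_T and 0.03 × s_C. The statistic is Z = (observed LiquiBand rate − observed control rate − 0.10) / SE, with SE taken from the maximum-likelihood estimates restricted to a difference of 0.10. Non-inferiority is declared if Z < −1.96. The false-claim probability is the sum of the two binomial probabilities over all pairs of counts that meet this rule.

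**Results, 113 per arm, all control recurrences detected.** Expected control events are 113 × 0.03 = 3.4.

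| LiquiBand detection | Observed LiquiBand rate | Expected LiquiBand events | Observed difference | False-claim probability |
|---|---|---|---|---|
| 100% | 13.0% | 14.7 | 10.0 points | 0.022 |
| 90% | 11.7% | 13.2 | 8.7 points | 0.050 |
| 80% | 10.4% | 11.8 | 7.4 points | 0.102 |
| 70% | 9.1% | 10.3 | 6.1 points | 0.195 |

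With full detection the test holds its nominal level. At 80% against 100% the error is about four times 0.025 (0.102 / 0.025 = 4.1).

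**Sensitivity.**
- Control recurrence from 1% to 10%, LiquiBand 10 points higher, 113 per arm: full detection gives 0.021 to 0.025; 80% against 100% gives 0.090 to 0.138.
- 142 per arm, 3% control, 80% against 100%: 0.114.
- 80% detection in **both** arms, 3% control, 113 per arm: 0.076. Equal misses shrink the absolute difference (10.4% − 2.4% = 8.0 points), so masking alone would not remove this part.

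**The case against.** **The blinded subject can raise a suspicion.** A reader might infer that a recurrence counts only if an unmasked clinician first suspects it. Table 1 does not support that: reports by the subject, who is blinded, are also evaluated. Its confirmation sentence can even be read as sending any reported suspicion to ultrasound. This narrows the exposure but does not close it. Physical examination precedes ultrasound in the wording, nothing says that a report must go forward if the examiner disagrees, and recurrences that the subject does not notice depend on the examiner.

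**The direction is not known.** Examiners could look harder at an unfamiliar device, which would work against LiquiBand. Nor do the documents say that the examiner is the operating surgeon; they say only that it is a clinician. Both objections stand. The point is that the ascertainment is unprotected, not that it is known to be biased.

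**A modest excess need not mislead.** A reader might infer that unequal referral could turn a LiquiBand disadvantage into an advantage, or yield a false claim at ordinary recurrence rates. Take assumed true rates of 6% and 3%, with 60% of LiquiBand and 90% of control recurrences referred. The observed rates are 6% × 0.60 = 3.6% and 3% × 0.90 = 2.7%. The excess falls from 3.0 to 0.9 points, so 2.1 / 3.0 = 70% of it is hidden, but its sign is kept. A true excess of 3 points also lies inside the 10-point margin, so a claim of non-inferiority would be correct. A false claim requires a true difference at or beyond the margin, which is why the working is set there.

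**The supplied text is partial.** A masking rule may exist elsewhere in the full protocol. That cannot be excluded.

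**Conclusion.** The point holds in limited form. Only the patient is named as blinded, ultrasound depends on suspicion, and the supplied text neither masks the examiner or reader nor guarantees that a subject's report reaches ultrasound. The exposed events are recurrences that the subject does not report and those dismissed at examination.

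The size is illustrative. At a true difference equal to the margin, a 10-point detection gap roughly doubles the nominal error and a 20-point gap roughly quadruples it. These figures rest on assumed recurrence and detection rates and on 113 per arm; the actual gap, if any, and its direction are unknown. A reader might also infer that the trial's main result is in doubt. It is not, on this ground: the primary endpoint is a VAS score given by the blinded patient. This is an inexpensive improvement to a confirmatory secondary endpoint.

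**What to change.** In Table 1 (Secondary Efficacy 1) and footnote 7, state for endpoint ascertainment that:

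1. every suspected recurrence reported by a subject goes to the ultrasound already planned, regardless of the examiner's opinion;
2. every examination meeting criteria that the investigators pre-specify, identical in both arms, goes there too;
3. the ultrasound request carries neither the device name nor the operative note;
4. the masked reading decides the endpoint.

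Where site staffing already allows, have the examination done by a clinician who did not perform the operation.

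The cost is revised wording, a masked request form and a few more ultrasounds, with no new staff. Some discretion remains, because the examiner still elicits and records the findings that meet the criteria; the change reduces the exposure rather than removing it. Fixed criteria should also reduce under-detection common to both arms. If a masking rule already exists in text not supplied here, citing it in Table 1 settles the masking part; the rule on subject reports would still need to be stated unless it too is already written.
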